4.0 TREATMENT PLAN

4.1 Study Design

This is a phase II open label single-arm study to evaluate the combination of nivolumab and ibrutinib in patients with CLL.

COHORT 1 and 3	C1D1	C1D15	C2D1	C2D15	C3D1 and then Q2 weeks for a total of 96 weeks	After 96 weeks
Nivolumab*	3 mg/kg IV	3 mg/kg IV	3 mg/kg IV	3 mg/kg IV	3 mg/kg IV	—
Ibrutinib	—	—	Begin 420 mg orally once daily			
COHORT 2						
Nivolumab*	3 mg/kg IV	3 mg/kg IV	3 mg/kg IV	3 mg/kg IV	3 mg/kg IV	—
Ibrutinib	On ibrutinib stable oral daily dose for >9 months with residual CLL (PR) at enrollment, continue at same ibrutinib daily dose					

*** Note: After 3 cycles of treatment, the frequency of nivolumab administration may be decreased to once every 4 weeks, in consultation with the study PI.**

Each cycle is 28 days. Nivolumab dosing may be delayed for up to 3 days to accommodate for holidays/patient travel. Patients will receive nivolumab (3mg/kg IV over approximately 1 hour) monotherapy for the first cycle to assess for monotherapy toxicities of nivolumab. Nivolumab will continue for up to 24 cycles (96 weeks; 48 infusions). For Cohort 1 and cohort 3, ibrutinib will be initiated from the start of course 2. Treatment with ibrutinib will continue until disease progression, study termination, or a patient experiences a toxicity that requires discontinuation of ibrutinib. For Cohort 2, patients will have been on ibrutinib for >9 months, and ibrutinib dosing should continue. Nivolumab will be initiated after consent is provided, eligibility confirmed, and all pretreatment studies are complete. For patients with RT – ibrutinib may be introduced earlier than start of cycle 2, in case of worsening disease, after discussion with study PI.

5.0 STUDY MEDICATIONS

5.1 Nivolumab (Anti-PD1)

Nivolumab is a fully human, IgG4 (kappa) isotype, monoclonal antibody that binds PD-1. Nivolumab will be supplied in vials of 100 mg (10 mg/mL) and packaged in an open-label fashion. See Appendix 1 for Pharmacy Reference Material.

5.1.1 Preparation and Dispensing of Nivolumab

The product storage manager should ensure that the study drug is stored in accordance with the environmental conditions (temperature, light, and humidity) as determined by the Investigator Brochure. If concerns regarding the quality or appearance of the study drug arise, do not dispense the study drug and contact the sponsor immediately.

Investigational product documentation must be maintained that includes all processes required to ensure drug is accurately administered. This includes documentation of drug storage, administration and, as applicable, storage temperatures, reconstitution, and use of required processes (e.g. required diluents, administration sets).

Nivolumab vials must be stored at a temperature of 2°C to 8°C and should be protected from light. If stored in a glass front refrigerator, vials should be stored in the carton. Recommended safety measures for preparation and handling of nivolumab include laboratory coats and gloves.

For details on prepared drug storage and use time of nivolumab under room temperature/light and refrigeration, please refer to the Investigator Brochure section for “Recommended Storage and Use Conditions”. Care must be taken to assure sterility of the prepared solution as the product does not contain any anti-microbial preservative or bacteriostatic agent. No incompatibilities between nivolumab and polyolefin bags have been observed.

Nivolumab is to be administered as an IV infusion over approximately 1 hour, using a volumetric pump with a 0.2/0.22 micron in-line filter at the protocol-specified dose. The drug can be diluted with 0.9% normal saline for delivery but the total drug concentration of the solution cannot be below 1 mg/ml. It is not to be administered as an IV push or bolus injection. At the end of the infusion, flush the line with a sufficient quantity of normal saline.

Unused or expired nivolumab vials will be disposed per MDACC guidelines.

5.1.2 Administration of Nivolumab

Patients will receive nivolumab as an IV infusion over approximately 1 hour. Dosing calculations should be based on the body weight assessed at the start of each cycle as described above. If the subject's weight on the day of dosing differs by > 10% from the weight used to calculate the original dose, the dose must be recalculated. All doses should be rounded to the nearest milligram. No doses of nivolumab may be given within 11 days of another.

5.1.3 Patient Monitoring During Infusion

For first dose, patient vital signs should be monitored prior to dosing, about 15 minutes after initiation

of the infusion (then every 15-20 minutes as indicated) and at 30 minutes after completion of the infusion, or longer if indicated, until the vital signs normalize or return to baseline. For subsequent infusions, vital signs should be collected prior to dosing and every 30 minutes during dosing.

5.1.4 Treatment of Nivolumab Related Infusion Reactions

Since nivolumab contains only human immunoglobulin protein sequences, it is unlikely to be immunogenic and induce infusion or hypersensitivity reactions. However, if such a reaction were to occur, it might manifest with fever, chills, rigors, headache, rash, pruritus, arthralgias, hypo- or hypertension, bronchospasm, or other symptoms. Infusion reactions should be graded according to NCI CTCAE (version 4.0) guidelines.

Treatment recommendations for nivolumab related infusion reactions are provided below and may be modified based on MD Anderson treatment standards and guidelines, as appropriate:

For Grade 1 symptoms (Mild reaction; infusion interruption not indicated; intervention not indicated): Remain at bedside and monitor subject until recovery from symptoms. The following prophylactic premedications are recommended for future infusions: diphenhydramine 50 mg (or equivalent) and/or acetaminophen 325 to 1000 mg at least 30 minutes before additional nivolumab administrations.

For Grade 2 symptoms (Moderate reaction requires therapy or infusion interruption but responds promptly to symptomatic treatment [e.g. antihistamines, non-steroidal anti-inflammatory drugs, narcotics, corticosteroids, bronchodilators, IV fluids]; prophylactic medications indicated for \leq 24 hours):

Stop the nivolumab infusion, begin an IV infusion of normal saline, and treat the subject with diphenhydramine 50 mg IV (or equivalent) and/or acetaminophen 325 to 1000 mg; remain at bedside and monitor subject until resolution of symptoms. Corticosteroid or bronchodilator therapy may also be administered as appropriate. If the infusion is interrupted, then restart the infusion at 50% of the original infusion rate when symptoms resolve; if no further complications ensue after 30 minutes, the rate may be increased to 100% of the original infusion rate. Monitor subject closely. If symptoms recur then no further nivolumab will be administered at that visit. Administer diphenhydramine 50 mg IV, and remain at bedside and monitor the subject until resolution of symptoms. The amount of study drug infused must be recorded on the case report form (CRF). The following prophylactic premedications are recommended for future infusions: diphenhydramine 50 mg (or equivalent) and/or acetaminophen 325 to 1000 mg should be administered at least 30 minutes before additional nivolumab administrations. If necessary, corticosteroids (recommended dose: up to 25 mg of IV hydrocortisone or equivalent) may be used.

For Grade 3 or Grade 4 symptoms [Severe reaction, Grade 3: prolonged (i.e. not rapidly responsive to symptomatic medication and/or brief interruption of infusion); recurrence of symptoms following initial improvement; hospitalization indicated for other clinical sequelae (e.g. renal impairment, pulmonary infiltrates), Grade 4: life- threatening; pressor or ventilatory support indicated]:

Immediately discontinue infusion of nivolumab. Begin an IV infusion of normal saline, and treat the

subject as follows: Recommend bronchodilators, epinephrine 0.2 to 1 mg of a 1:1,000 solution for subcutaneous administration or 0.1 to 0.25 mg of a 1:10,000 solution injected slowly for IV administration, and/or diphenhydramine 50 mg IV with methylprednisolone 100 mg IV (or equivalent), as needed. Subject should be monitored until the investigator is comfortable that the symptoms will not recur. Nivolumab will be permanently discontinued. Institutional guidelines will be followed for the treatment of anaphylaxis. Remain at bedside and monitor subject until recovery from symptoms. In the case of late-occurring hypersensitivity symptoms (e.g. appearance of a localized or generalized pruritus within 1 week after treatment), symptomatic treatment may be given (e.g. oral antihistamine or corticosteroids).

5.2 Ibrutinib

Ibrutinib is a small-molecule inhibitor of BTK. Ibrutinib forms a covalent bond with a cysteine residue in the BTK active site, leading to inhibition of BTK enzymatic activity. Ibrutinib 420 mg will be administered orally once daily. Ibrutinib should be administered with 8 ounces (approximately 240 mL) of water. The capsules should be swallowed intact and patients should not attempt to open capsules or dissolve them in water. Each dose of ibrutinib should be taken approximately 2 hours after a meal or at least 30 minutes before the next meal, at approximately the same time each day. If a dose of ibrutinib is not taken at the scheduled time, it can be taken as soon as possible on the same day with a return to the normal schedule the following day. Extra capsules of ibrutinib should not be taken to make up for the missed dose.

Concomitant use of strong CYP3A inhibitors which would be taken chronically (e.g., ritonavir, indinavir, nelfinavir, saquinavir, boceprevir, telaprevir, nefazodone) is not recommended. Concomitant use of strong CYP3A inducers (e.g., rifampin, rifabutin, phenytoin, carbamazepine, and St. John's Wort) are not recommended. Avoid grapefruit and Seville oranges during ibrutinib treatment, as these contain moderate inhibitors of CYP3A. Please see Section 6.2 for more details.

5.2.1 How Supplied

Supplied as 140mg capsules

5.2.2 Stability

Store bottles at room temperature 20°C to 25°C

5.2.3 Pharmacokinetics

Absorption: Ibrutinib is absorbed after oral administration with a median Tmax of 1 to 2 hours. Ibrutinib exposure increases with doses up to 840 mg. The steady-state AUC (mean \pm standard deviation) in patients at 420 mg is 680 ± 517 ng·h/mL. Administration with food increased ibrutinib AUC by approximately 2-fold.

Distribution: Reversible binding of ibrutinib to human plasma protein in vitro was 97.3%.

Metabolism: Metabolism is the main route of elimination for ibrutinib. It is metabolized to several metabolites primarily by cytochrome P450, CYP3A, and to a minor extent by CYP2D6. The active metabolite, PCI-45227, is a dihydrodiol metabolite with inhibitory activity towards BTK approximately 15 times lower than that of ibrutinib.

Elimination: The half-life of ibrutinib is 4 to 6 hours. Ibrutinib, mainly in the form of metabolites, is

eliminated primarily via feces.

Renal Impairment: Ibrutinib is not significantly cleared renally; urinary excretion of metabolites is < 10% of the dose. Creatinine clearance > 25 mL/min had no influence on the exposure to ibrutinib. There are no data in patients with severe renal impairment (creatinine clearance < 25 mL/min) or in patients on dialysis.

Hepatic Impairment: Ibrutinib is metabolized in the liver. No clinical trials have been completed in patients with impaired hepatic function.

6.0 DOSE DELAYS AND MODIFICATIONS

Patients who experience Grade 3 or 4 toxicity that can be clearly attributed to either nivolumab or to ibrutinib may continue treatment with the other agent while the causative agent is delayed until resolution of toxicity to grade ≤1 or baseline. In cases where Grade 3 or 4 toxicity cannot be attributed to a specific study drug, both study drugs should be held regardless of attribution of toxicity until the toxicity is resolved to grade ≤1 or baseline. Grade 3 or 4 nivolumab immune-related toxicities will generally result in discontinuation of nivolumab, leaving ibrutinib monotherapy.

6.1 Dose modification for nivolumab

Dose reductions or dose escalations are not permitted.

6.1.1 Pulmonary adverse events

Pulmonary AEs have been observed following treatment with nivolumab and have occurred after a single dose and after as many as 48 treatments. The majority of cases reported were Grade 1 or Grade 2 and patients presented with either asymptomatic radiographic changes (eg, focal ground glass opacities, patchy infiltrates) or with symptoms of dyspnea, cough, or fever. Early recognition and treatment of pneumonitis is critical to its management. Patients should be advised to seek medical evaluation promptly if they develop new onset dyspnea, cough or fever or if they have worsening of these baseline symptoms. As respiratory symptoms are common in patients with CLL, it is important that an evaluation/work-up distinguish between non-drug-related causes (eg, infection, progression of disease) and a possible drug-related pulmonary toxicity as the management of these events is quite different. Rule out non-inflammatory causes. If non-inflammatory cause, treat accordingly and continue therapy.

Grade of Pneumonitis	Management	Follow-up
Grade 1 (Asymptomatic; clinical or diagnostic observations only; intervention not indicated)	
Consider delay of nivolumabMonitor for symptoms every 2-3 daysConsider Pulmonary and ID consults	
Re-image at least every 3 weeks.If worsens:
Treat as Grade 2 or 3-4
Grade 2 (Symptomatic; medical intervention indicated; limiting instrumental ADL)	
Delay nivolumabPulmonary and ID consultsMonitor symptoms daily, consider hospitalizationSteroids: 1 mg/kg/day	
Re-image every 1-3 daysIf improves:
When symptoms return to near baseline, taper steroids over at least 1 month and then resume nivolumab

	
 methyl-prednisolone IV or oral equivalent Consider bronchoscopy, lung biopsy 	If not improving after 2 weeks or worsening: 
 Treat as Grade 3-4
Grade 3 (Severe symptoms; limiting self-care ADL; oxygen indicated) or Grade 4 (Life-threatening respiratory compromise; urgent intervention indicated [e.g., tracheotomy or intubation])	
 Discontinue Nivolumab Hospitalize Pulmonary and ID consults Steroids: 2-4 mg/kg/day methylprednisolone IV or IV equivalent Add prophylactic antibiotics for opportunistic infections Consider bronchoscopy, lung biopsy 	If improves to baseline: 
 Taper steroids over at least 6 weeks If not improving after 48 hours or worsening: 
 Add additional immunosuppression (e.g. infliximab, cyclophosphamide, IVIG, or mycophenolate mofetil)

Patients on IV steroids may be switched to an equivalent dose of oral corticosteroids (e.g. prednisone) at start of tapering or earlier, once sustained clinical improvement is observed.

6.1.2 Gastrointestinal adverse events

Gastrointestinal AEs have been observed following treatment with nivolumab. Most cases of diarrhea were low grade (Grade 1-2). Colitis occurs less frequently than diarrhea. High grade cases of diarrhea and colitis were managed with corticosteroids and in all cases the events resolved. Early recognition and treatment of diarrhea and colitis are critical to its management. Patients should be advised to seek medical evaluation if they develop new onset diarrhea, blood in stool, or severe abdominal pain, or if they have worsening of baseline diarrhea. As GI symptoms are common in patients with CLL, it is important that an evaluation/work-up distinguish between non-drug-related causes (eg, infection, progression of disease) and a possible drug-related AE as the management is quite different. Rule out non-inflammatory causes. If non-inflammatory cause is identified, treat accordingly and continue nivolumab therapy. Opiates/narcotics may mask symptoms of perforation.

NOTE: As diarrhea could occur from the use of ibrutinib, patients with grade 2 diarrhea should have their ibrutinib held as well.

Grade of Diarrhea/Colitis	Management	Follow-up
Grade 1 Diarrhea (Increase of <4 stools per day over baseline) Colitis (Asymptomatic)	
 Continue nivolumab Symptomatic treatment 	
 Close monitoring for worsening symptoms If worsens: 
 Treat as Grade 2 or 3-4
Grade 2 Diarrhea (Increase of 4 - 6 stools per day over baseline) Colitis (Abdominal pain; blood in stool)	
 Delay nivolumab Symptomatic treatment 	If improves to grade 1: 
 Resume nivolumab If persists > 5-7 days or recur: 
 Steroids: 0.5-1.0 mg/kg/day methylprednisolone or oral equivalent When symptoms improve to grade 1, taper steroids over

		
at least 1 month, consider prophylactic antibiotics for opportunistic infections, and resume nivolumab
 
If worsens or persists > 3-5 days with oral steroids:
 
 ▪ Treat as Grade 3/4

Grade 3
 
Diarrhea (Increase of >=7 stools per day over baseline; incontinence; hospitalization indicated; interfering with ADL)
 
Colitis (Severe abdominal pain; medical intervention indicated; peritoneal signs)
 
Grade 4
 
Diarrhea (Life-threatening consequences; urgent intervention indicated)
 
Colitis (Life-threatening consequences; urgent intervention indicated; perforation)
	
 ▪ Discontinue Nivolumab ▪ Steroids: 1-2 mg/kg/day methylprednisolone IV or IV equivalent ▪ Add prophylactic antibiotics for opportunistic infections ▪ Consider sigmoidoscopy or colonoscopy 	
If improves:
 
 ▪ Continue steroids until grade 1, then taper over at least 1 month 
If persists >3-5 days, or recurs after improvement:
 
 ▪ Add infliximab (if no contraindication). Note: Infliximab should not be used in cases of perforation or sepsis

Patients on IV steroids may be switched to an equivalent dose of oral corticosteroids (e.g. prednisone) at start of tapering or earlier, once sustained clinical improvement is observed.

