6.1.5 Skin adverse events

Rash and pruritus are the most common skin AEs observed following treatment with nivolumab. The rash is typically focal with a maculopapular appearance occurring on the trunk, back, or extremities. Most cases have been low or moderate grade. In some cases, rash and pruritus resolved without intervention. Topical corticosteroids have been used for some cases of rash. Anti-histamines have been used for some cases of pruritus. More severe cases responded to systemic corticosteroids. Patients should be advised to seek medical evaluation if they notice new onset rash. Early consultation with a dermatology specialist and a biopsy should be considered if there is uncertainty as to the cause of the rash or if there is any unusual appearance or clinical feature associated with it. Other drugs which may cause rash should be considered in the differential and if possible discontinued.

Grade of Rash	Management	Follow-up
Grade 1-2 (Covering ≤ 30% of BSA)	
 Continue nivolumab Symptomatic therapy 	
If persists > 1-2 weeks or recurs:
 
 Consider skin biopsy

	(e.g. antihistamines, topical steroids)	
 Delay nivolumab Steroids: Consider 0.5-1.0 mg/kg/day methylprednisolone IV or oral equivalent. Once improving, taper steroids over at least 1 month, consider prophylactic antibiotics for opportunistic infections, and resume nivolumab 
If worsens:
 
 Treat as Grade 2 or 3-4
Grade 3-4 (Covering >30% BSA; Life threatening consequences)	
 Delay or discontinue nivolumab Consider skin biopsy Dermatology consult Steroids: 1-2 mg/kg/day IV methylprednisolone IV or IV equivalent 	
If improves to Grade 1:
 
 Taper steroids over at least 1 month and add prophylactic antibiotics for opportunistic infections Resume nivolumab

Patients on IV steroids may be switched to an equivalent dose of oral corticosteroids (e.g. prednisone) at start of tapering or earlier, once sustained clinical improvement is observed.

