6.1.11 Criteria to Resume Treatment

Patients may resume treatment with study drug when the drug-related AE(s) resolve to Grade ≤1 or baseline value, with the following exceptions:

- Patients may resume treatment in the presence of Grade 2 fatigue
- Patients who have not experienced a Grade 3 drug-related skin AE may resume treatment in the presence of Grade 2 skin toxicity
- Patients with baseline Grade 1 AST/ALT or total bilirubin who require dose delays for reasons other than a 2-grade shift in AST/ALT or total bilirubin may resume treatment in the presence of Grade 2 AST/ALT OR total bilirubin
- Patients with combined Grade 2 AST/ALT AND total bilirubin values meeting discontinuation parameters (Discontinuation Section, Section 12.0) should have treatment permanently discontinued
- Drug-related pulmonary toxicity, diarrhea, or colitis, must have resolved to baseline before treatment is resumed
- Drug-related endocrinopathies adequately controlled with only physiologic hormone replacement may resume treatment

If the criteria to resume treatment are met, the subject should restart treatment at the next scheduled timepoint per protocol. However, if the treatment is delayed past the next scheduled timepoint per protocol, the next scheduled timepoint will be delayed until dosing resumes.

If treatment is delayed > 6 weeks, the subject must be permanently discontinued from study therapy, except as specified in discontinuation section.

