12.0 DISCONTINUATION OF STUDY TREATMENT

A patient's treatment with study drugs may be discontinued for any of the following reasons:

- Clinically significant progressive disease
- Adverse events that are not manageable with dose adjustments and/or optimal medical management, or that, in the opinion of the investigator, pose an unacceptable risk for the patient.
- Investigator decision
- Patient decision (e.g., withdrawal of consent)
- Study termination by Sponsor

Patients who experience toxicity that can be clearly attributed to either nivolumab or to ibrutinib may continue treatment with the other agent. If toxicity cannot be clearly attributed to a single agent, treatment with both agents should be discontinued. Patients who discontinue treatment for reasons other than progressive disease should remain on study and continue to have disease assessments per protocol.

Additional Discontinuation Criteria for Nivolumab

Treatment should be permanently discontinued for the following:

- Any Grade 2 drug-related uveitis or eye pain or blurred vision that does not respond to topical therapy and does not improve to Grade 1 severity within the re-treatment period OR requires systemic treatment
- Any Grade 3 non-skin, drug-related adverse event lasting > 7 days, with the following exceptions for drug-related laboratory abnormalities, uveitis, pneumonitis, bronchospasm, diarrhea, colitis, neurologic adverse event, hypersensitivity reactions, and infusion reactions

- Grade 3 drug-related uveitis, pneumonitis, bronchospasm, diarrhea, colitis, neurologic adverse event, hypersensitivity reaction, or infusion reaction of any duration requires discontinuation
- Grade 3 drug-related laboratory abnormalities do not require treatment discontinuation except those noted below:
 - Grade 3 drug-related thrombocytopenia > 7 days or associated with bleeding requires discontinuation
 - Any drug-related liver function test (LFT) abnormality that meets the following criteria require discontinuation:
 - AST or ALT > 8 x ULN
 - Total bilirubin > 5 x ULN
 - Concurrent AST or ALT > 3 x ULN and total bilirubin > 2 x ULN
- Any Grade 4 drug-related adverse event or laboratory abnormality, except for the following events which do not require discontinuation:
 - Isolated Grade 4 amylase or lipase abnormalities that are not associated with symptoms or clinical manifestations of pancreatitis and decrease to < Grade 4 within 1 week of onset.

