 - Isolated Grade 4 electrolyte imbalances/abnormalities that are not associated with clinical sequelae and are corrected with supplementation/appropriate management within 72 hours of their onset
- Any dosing interruption lasting > 6 weeks with the following exceptions:
 - Dosing interruptions to allow for prolonged steroid tapers to manage drug-related adverse events are allowed. Prior to re-initiating treatment in a subject with a dosing interruption lasting > 6 weeks, the Investigator must be consulted. Tumor assessments should continue as per protocol even if dosing is interrupted
 - Dosing interruptions > 6 weeks that occur for non-drug-related reasons may be allowed if approved by the Investigator. Prior to re-initiating treatment in a subject with a dosing interruption lasting > 6 weeks, the Investigator must be consulted. Tumor assessments should continue as per protocol even if dosing is interrupted
- Any adverse event, laboratory abnormality, or intercurrent illness which, in the judgment of the Investigator, presents a substantial clinical risk to the subject with continued nivolumab dosing

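### The Grade 2 diarrhea/colitis and pneumonitis rows allow nivolumab to be resumed short of the baseline that Section 6.1.11 requires, and two other rows offer an option that Section 12.0 forbids

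*Combined protocol and SAP*

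**What the plan says.** **Diarrhea/colitis.** The Grade 2 row of Section 6.1.2 delays nivolumab and gives two routes back. The first resumes it on the condition "If improves to grade 1". The second, for persistent or recurrent symptoms, uses steroids: "When symptoms improve to grade 1, taper steroids over" at least a month, and then resume. The Grade 1 row of that table reads "Diarrhea (Increase of <4 stools per day over baseline". Section 6.1.11 sets a general standard of Grade 1 or less, or baseline, and then lists this exception: "Drug-related pulmonary toxicity, diarrhea, or colitis, must have resolved to baseline before treatment is resumed".

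**Pneumonitis.** The Grade 2 row of Section 6.1.1 starts the steroid taper when symptoms are close to baseline, and resumes nivolumab after the taper.

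**Rash.** Section 6.1.5 puts two grades in one row, "Grade 3-4 (Covering >30% BSA; Life threatening consequences", with the action "Delay or discontinue nivolumab" and a resume step on improvement to Grade 1. Section 12.0 lists as grounds for permanent discontinuation: "Any Grade 4 drug-related adverse event or laboratory abnormality, except for the following events which do not require discontinuation". Only two exceptions follow. One is for isolated amylase or lipase changes and the other begins "Isolated Grade 4 electrolyte imbalances/abnormalities that are not associated with clinical sequelae". Skin is not among them.

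**Liver tests.** The Grade 3-4 row of Section 6.1.3 says to discontinue, with a note that nivolumab may be delayed instead if AST/ALT are at most 8 x ULN and bilirubin at most 5 x ULN. Section 12.0 also requires a permanent stop for AST or ALT above 3 x ULN together with bilirubin above 2 x ULN. The Grade 2 row repeats that concurrent rule; the Grade 3-4 row does not.

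**The concern.** The organ tables are what a clinician consults when an event occurs. If they are more lenient than the resume and stop rules elsewhere, the treatment a patient receives depends on which section is open. A patient could be re-dosed with bowel or lung toxicity that has not cleared, re-treated after a life-threatening rash, or kept eligible for nivolumab with a pattern of liver injury that Section 12.0 treats as a stop.

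Nothing in the protocol settles the order. Section 6.0 says only that Grade 3 or 4 immune-related toxicity generally ends nivolumab. Section 6.1.11 refers to the discontinuation section only for combined Grade 2 liver values and for delays over 6 weeks. The one clause on discordant text, in Section 11.1.2, covers recording and reporting of adverse events, not dosing.

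**Working it through.** The plan gives no figure on this point, so the check is a row-by-row comparison.

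1. **Grade 2 diarrhea/colitis.** Table: resume at Grade 1, which for diarrhea means up to 3 extra stools a day over baseline. Section 6.1.11: resume only at baseline. For a patient who has improved to Grade 1 but is not at baseline, the first branch says resume and 6.1.11 says wait. Both cannot be followed. The steroid branch does not re-dose at once, but it never asks for baseline at the end of the taper.

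2. **Grade 2 pneumonitis.** Table: taper when close to baseline, then resume. Section 6.1.11: pulmonary toxicity must be at baseline. The table again omits the final check.

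3. **Rash.** Grade 3 is consistent throughout: Section 6.1.10 delays for it, and the Grade 3 rule in Section 12.0 is limited to non-skin events. Only the Grade 4 part of the row differs from Section 12.0.

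4. **Liver tests.** The isolated cut-offs agree, since 8 x and 5 x ULN appear in both places. The difference lies where the delay note and the concurrent rule overlap within the Grade 3-4 row:
   - AST/ALT above 5 and up to 8 x ULN with bilirubin above 2 and up to 5 x ULN; or
   - AST/ALT above 3 and up to 8 x ULN with bilirubin above 3 and up to 5 x ULN.

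   Read from the table alone, AST 3.5 x with bilirubin 2.5 x ULN (Grade 2) must stop, while the worse case of AST 6 x with bilirubin 4 x ULN may be delayed.

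**Scale for diarrhea.** Inputs are from Table 2.4.2.4-1 (nivolumab monotherapy in solid tumors) and the maximum enrolment of 72 in Section 14.0.
- Treatment-related diarrhea, all doses: 41 any grade minus 3 Grade 3-4 = 38 Grade 1-2.
- 38/306 = 12.42% (Clopper-Pearson 95% CI 8.94% to 16.64%).
- 72 x 0.1242 = 8.9 patients (6.4 to 12.0).
- At 3 mg/kg, this trial's dose: 6/54 = 11.11% (4.19% to 22.63%); 72 x 0.1111 = 8.0 (3.0 to 16.3).
- If all three cohorts stopped after their first 9 patients: 27 x 0.1242 = 3.4.

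The table does not separate Grade 1 from Grade 2, so these figures do not count patients who would meet the conflict. For the liver row, 4/306 had Grade 3-4 related hepatic events (2/54 at 3 mg/kg), but the share with concurrent elevation is not given. Grade 3-4 related rash was 0/306.

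**The case against.** The strongest reply is that a careful investigator can comply with everything. Section 12.0 presents its nivolumab list as additional criteria. The rash row already includes discontinuation as a choice, and the liver row makes it the default with delay only permitted. A permission does not contradict a mandatory stop elsewhere. That stands: a reader might infer that the rash and liver rows flatly contradict Section 12.0, and the documents do not support it. They offer an option that Section 12.0 forbids, without warning. The Grade 3-4 liver row also has no resume step of its own, which limits the harm there.

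On diarrhea, the reply is that nivolumab already continues in patients who never exceed Grade 1, so mild symptoms above baseline are tolerated, and that 6.1.11, being the section on resuming and worded as an obligation, naturally controls. The first part makes the harm modest. The second is a reasonable reading, but the protocol does not state it, and 6.1.11 singles out these events for a stricter standard than its general rule. In the steroid branches the 6.1.11 check could be made at the end of the taper, so those are omissions rather than instructions to re-dose early.

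All nivolumab is given at one centre (Section 9.0), and Section 12.0 lets the investigator stop for substantial risk. Both reduce the danger, but neither says which rule applies.

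**Conclusion.** The diarrhea/colitis conflict is direct, and the pneumonitis row has the same mismatch with 6.1.11. The rash point is confined to Grade 4 and the liver point to concurrent elevation; both are gaps that the stricter choice closes. The sponsor should correct all four, because they concern re-dosing after immune toxicity.

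The size is uncertain. About 9 patients with Grade 1-2 related diarrhea assumes full enrolment of 72 and that the solid-tumor monotherapy rate carries over. Ibrutinib causes diarrhea of its own (Section 2.5.2), so the figure may be low. A reader might take 9 as the number exposed to the conflict. It is not: only the Grade 2 share is relevant, and the documents do not give it. Nor does the point reach the efficacy conclusions, the sample size or the toxicity stopping boundaries; the effect is on individual patient safety only.

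**What to change.** Four row edits and one sentence:

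- **Section 6.1.2, Grade 2:** require baseline before nivolumab is resumed, in both branches.
- **Section 6.1.1, Grade 2:** require baseline before nivolumab is resumed after the taper.
- **Section 6.1.5:** give Grade 4 rash its own row with permanent discontinuation and no resume step, as the renal table does for Grade 4. Grade 3 can stay as it is.
- **Section 6.1.3, Grade 3-4:** add to the delay note: unless AST or ALT >3 x ULN with total bilirubin >2 x ULN, in which case discontinue.
- **Section 6.1, once:** where the organ tables, 6.1.10, 6.1.11 and Section 12.0 differ, the stricter rule governs.

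The last sentence should not say that 6.1.11 and Section 12.0 prevail over the tables. That would loosen rules where a table is stricter: Grade 2 neurologic events and Grade 2 liver tests without steroids resume only at baseline in their tables, but at Grade 1 under the general rule of 6.1.11. Creatinine elevation of Grade 2-3 lasting over 7 days is handled as Grade 4 in Section 6.1.6, whereas Section 12.0 does not require a stop for it.

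The cost is amendment wording, plus a few patients who resume later or stop nivolumab.
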